Phase I & II, Aim 2: Clients attending the syringe exchange will be invited to participate in the RCT by a research staff. Clients who agree to participate will provide signed informed consent via Qualtrics, and participants that consent will be randomized to the intervention or control condition via Qualtrics. At the time of consent, the research staff will review the consent with the participant before they sign it to ensure that the participant is clear about data will be obtained by National Institutes of Health and Duke Clinical Research Institute versus the UO. Specifically, the UO will collect identifying information like including name and date of birth to improve the ability to link data over time and will also collect contact information. The research staff will clarify that the information that the participant shared with the UO research team will be used by National Institutes of Health (NIH) and Duke Clinical Research Institute (DCRI), however identifying information will not be shared with NIH or Duke. At the time of consent, the research team member will ask clients to complete and a HIPAA Authorization form (also in Qualtrics) for the purpose of releasing their testing and vaccination intake data and test results to the UO research team. Clients will be given a blank paper copy consent and HIPAA form. For follow-up surveys, clients will be reminded that they previously consented to participating in a research study when they were tested and remind them that participation in the follow up survey is voluntary.

Staff and volunteer co-creation. For pre-post training surveys consent forms for HIVA staff and volunteers will be provided on Qualtrics. The informed consent will explain the project, their rights, and how the data will be used in the future. Staff and volunteers will be assured that their participation in the study is voluntary and that if they choose to participate, they can change their minds at any time. They will be informed about potential benefits and harm. Staff and volunteers will be informed that their data will only be presented in aggregate. Staff and volunteers will provide signed informed consent before participating. Participants will be able to download from Qualtrics and save a copy of the consent for their records. It will be clear that they will receive compensation for attending training, regardless of their participation in the survey.

Phase I & II, Aim 3: Survey and interview data from HIVA staff and volunteers. For survey and qualitative interview data on implementation experiences from HIVA staff and volunteers, consent forms for HIVA staff and volunteers will be provided on Qualtrics. The informed consent will explain the project, their rights, and how the data will be used in the future. Staff and volunteers will be assured that their participation in the study is voluntary and that if they choose to participate, they can change their minds at any time. They will be informed about potential benefits and harm. Staff and volunteers will be informed that their data will only be presented in aggregate. Staff and volunteers will provide signed informed consent before participating. Participants will be able to download from Qualtrics and save a copy of the consent for their records. In addition to asking for consenting purposes, we will ask for an email address for sending them a \$50 gift card. The consent explains that we will use names to link survey and audio transcript data. In the consent, we also indicate that after sending the gift card and linking audio and survey data, a unique ID will be assigned to survey data and audio transcript and then identifiers (name and email) will be permanently deleted.

Emails with the consent and survey will be sent to staff and volunteer by HIVA. If staff and volunteers choose to participate, after reviewing and signing informed consent, they will be able to proceed to the survey; after completing the survey they will have the opportunity to schedule a time for a qualitative interview. In the consenting process, participants will provide their name and signature. However, names will be replaced with a unique participant ID and consent information will be stored separately from the data. Qualitative interview data will be audio-recorded but names will not be used in the interview to protect anonymity of responses. Audio recordings will be transcribed for coding. Participants' names will be used to link their survey and their audio transcript so we can know participants to whom we should send a gift card for their participation. After this, a unique ID will be assigned to participants' survey data and audio transcript to link these and then identifiers (name and email) will be permanently deleted. The audio transcription of the interview will be stored on a secure server, prior to being transcribed, and will be destroyed immediately following transcription. All staff and volunteer data will be presented in aggregate so that responses can never be linked to a particular staff or volunteer.

Additional consent procedures will be added in a subsequent amendment for new research activities.

Testing and Vaccine Hesitancy Client Interviews: The research assistant will provide a printed copy of the “client interviews informed consent document” for the individual to read. The research assistant will request that the individual does not sign the consent form until they have had a conversation with the research assistant regarding the form’s contents. After the individual has finished reading the document, the research assistant will go over every element with them and will administer several comprehension checks to ensure there is a mutual understanding of what will be asked of them during the interview. During the process of obtaining informed consent, the research assistant will also ensure that the participant understands that their interview responses may also be shared with HIV Alliance and a research team at the Prevention Science Institute. Specific attention will be drawn to the fact that their participation in the study will have no bearing on their ability to access HIV Alliance resources. Once the research assistant feels confident that the participant understands the entirety of the document, they will ask them to sign the final page and the interview will proceed. The research assistant will remind them that they are welcome to ask questions at any point during the interview process or after the interview has completed.

F. Provisions for Participant Privacy and Data Confidentiality

Table 2. Identifiable information table

Component	Source	Purpose
Phase II, Aim 1 Testing	HIV Alliance Intake, created and prepared for MAP to process samples by [name] (only individuals who consent to sharing are retained for study purposes)	Linking data over time to ensure participants have previously consented when conducting the follow-up survey, ability to re-contact for follow-up survey
Phase II, Aim 1 Testing Result	MAP	Linking data over time to ensure participants have previously consented when conducting the follow-up survey, satisfying funding requirements
Phase II, Aim 1 Vaccination	HIV Alliance Intake only for people who consent created and managed by [name]	Linking data over time to ensure participants have previously consented when conducting the follow-up survey, ability to re-contact for follow-up survey
Phase II, Aim 1 Follow-up Survey	RA administered survey	Linking data over time, required by the funder to collect but not to share (funding could be removed if not collected)
Phase II, Aim 2 Staff and Volunteer	RA administered survey	Linking pre-post data over time (completed)
Phase II, Aim 2 Intervention Enrollment	RA administered survey	Linking data over time to ensure participants have previously consented when conducting the follow-up survey, ability to re-contact for follow-up survey
Phase II, Aim 2 Intervention Follow-up Survey	RA administered survey	Linking data over time, required by the funder to collect but not to share (funding could be removed if not collected)
Phase II, Aim 2 Testing	HIV Alliance Intake, created and prepared for MAP to process samples by [name] (only individuals who consent to sharing are retained for study purposes)	Linking data over time to ensure participants have previously consented when conducting the follow-up survey, ability to re-contact for follow-up survey

Phase II, Aim 2 Testing Result	MAP	Linking data over time to ensure participants have previously consented when conducting the follow-up survey, satisfying funding requirements
Phase II, Aim 2 Vaccination	HIV Alliance Intake only for people who consent created and managed by [name]	Linking data over time to ensure participants have previously consented when conducting the follow-up survey, ability to re-contact for follow-up survey

1. Privacy

Common data elements survey data from syringe exchange participants will be provided to the Coordination and Data Collection Center (CDCC). Data will only be shared with CDCC if syringe exchange participants consent to participate in the study. Data from all syringe exchange participants that consent to the study will be shared. Common data elements data will be shared using secure processes and procedures as designated by the CDCC. No data from HIVA staff and volunteers will be shared. The research team will not have access to HIVA SSP client protected health information, other than the data described in the methods, materials and assessment section.

2. Data Disposition

For all identifiable data, consents and HIPAA Authorization are programmed with the survey questions but identifying information (names on consent/HIPAA) will be stripped from the data at earliest opportunity. All data will be retained and stored for the duration of record storage but will be de-identified with a "code key" following study completion by assigning a new ID to the data. This code key will be kept separate from the data and the de-identified data on the secure file server at the Prevention Science Institute and destroyed within 1 year of study completion to ensure all data are cleaned and there is no loss of linked data. Data will be maintained by the research study team. Data will be transmitted between the research team and UO COVID-19 MAP lab and between the research team and HIVA using encrypted, secure email. Data will only be transmitted for participants for whom the research team has consent and HIPAA authorization for sharing of testing data.

3. Confidentiality

Data will be de-identified meaning anything used to identify someone will be stored in a separate secured data file that is only accessible by the data manager to link study records and individuals who need to recontact the participant for the follow-up survey. Identifiers will be stored for 1-year after data collection is complete which is the earliest opportunity for being destroyed to ensure all data files are complete and accurately linked and then destroyed. UO's COVID-19 MAP will only give the research team access to testing data for people for whom we have a HIPAA authorization and consent. All research survey data and audio files will be stored at the Prevention Science Institute using standard security techniques (password protected file folders on the University's Prevention Science Institute secure server). Data from Qualtrics will only be accessed using secure wifi.

Storage of data will be stored electronically on a private server and will be directly uploaded only while using secure wifi. If the data must be transferred, they will be transferred using a secure client server. Study researchers and the students they supervise may be granted access to the de-identified data after signing a data use agreement, in order to complete analyses. Records will be kept for up to 3 years after the study has been completed.

Research funded by NIH automatically has a Certificate of Confidentiality associated with it. This is added protection against forced disclosure of research information in circumstances of subpoena.

G. Potential Research Risks or Discomforts to Participants

Potential Risks: Potential risks and discomforts involved in participation include (1) possible violation of confidentiality. This risk are unlikely but possible.

Minimizing Potential Risk 1: Possible violation of confidentiality. All records obtained from participants will be kept strictly confidential. To ensure strict confidentiality, any additional data will be coded with HIVA ID.

The protocol involves intervention. The intervention includes an intervention that aims to increase testing and vaccination utilization. This will involve a brief assessment and conversation with syringe exchange staff or volunteers. This research does not pose any additional risk over the services provided as usual.

The funding agency required a Data Safety Monitoring Plan for this research at the time of funding proposal. A copy of the DSMP submitted to the funder is attached.

There is no established Data and Safety Monitoring Board/Committee (DSMB/C) as noted in the DSMP.

H. Potential Benefits of the Research

The overall risk involved in the project is relatively minor, given the goals of the research. Participants would face similar levels of risk -or higher - visiting a clinic or other outdoor testing or vaccination event in order to be tested or vaccinated for COVID-19. Participants will benefit by receiving a free SARS-CoV-2 diagnostic test and educational information that could improve their health behaviors and reduce transmission of SARS-CoV-2 in their communities and around Oregon. Others in the community would benefit if participants are identified as positive who previously did not know they were infectious and if participants actively alter their health behaviors, whether infectious or not.

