Clients using HIVA's syringe exchange services provide their unique HIVA ID. This unique identifier is used to link data for persons who are repeat users of HIVA's services. We will use the unique ID to link HIVA intake, CDE data, and UO's CLIA laboratory data (i.e., testing utilization) for the purpose of evaluating effects of Connect2Test on testing utilization and the moderating effects of SDOHs (assessed using the CDEs and HIVA intake data).

At the time of consent, a research team member will ask clients to complete a HIPAA Authorization form (which will be programmed in Qualtrics with the consent and survey) for the purpose of releasing their testing utilization data to the UO research team. UO's COVID-19 MAP will only give the research team access to testing utilization data for HIVA IDs for whom we have a HIPAA authorization and consent. The client will also be given a blank paper copy of the HIPAA Authorization form for this study.

During the course of the RCT, clients will only be invited to participate in the study once. Participation in the study will be tracked by research staff. Regardless of whether clients consent to participate in the study, they will be offered an opportunity to get tested every time they visit the exchange.

Data Analysis: We will use a randomized control trial to evaluate whether Connect2Test increases COVID-19 testing utilization. We will also test whether SDOH moderate intervention effects. We will use chi-square tests to examine whether the expected rates of testing utilization vary by condition. We will use logistic regression to examine whether SDOHs moderate intervention effects.

Phase II, Aim 2: For Aim 2, we will adapt the ME Connect2Test intervention that we developed during Phase I and examine whether the adapted Connect2Test augments the effects of Contingency Management on SARS-CoV-2 testing and vaccination utilization.

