Intervention testing. For Aim 2, we will use a randomized control trial (RCT) design to evaluate if this intervention in conjunction with contingency management increases COVID-19 testing and vaccination utilization, in comparison to contingency management (CM) alone. Aim 2 will be implemented at HIV Alliance syringe exchange sites. During client participation in syringe exchange services, clients will be invited to participate in the RCT by the research team member on site. Clients that agree to participate will complete signed informed consent programmed in Qualtrics; consented participants will complete a brief survey (Aim 2 Brief Client Survey) and be randomized by Qualtrics to the Connect2Test + CM condition or to CM alone. At the time of consent, research staff will ask clients to complete a HIPAA Authorization form for the purpose of sharing their testing and vaccination utilization data as well as test result with the UO research team. The HIPAA Authorization form will also be programmed in Qualtrics. Research staff will discretely inform syringe exchange staff/volunteers whether the client has been assigned to Connect2Test + CM so the staff/volunteer will know whether to deliver the intervention. Clients in the CM only condition will be invited to participate in testing and vaccination after completing syringe exchange. Clients in the Connect2Test + CM condition will receive the brief intervention, which involves an approximately 5-minute conversation guided by motivational

interviewing processes, and then be invited to participate in testing and vaccination. The syringe exchange staff/volunteer delivering the intervention as well as the research staff assisting with Aim 2 will also complete a checklist to document intervention delivery.

We will use data collected during testing and vaccination intake, "Testing Intake Form", processed by our study team's data scientist which includes name, date of birth, and contact information. We will collect test results from the UO COVID-19 MAP laboratory. At the time of testing or vaccination, the HIVA testing facilitator will invite clients to complete the testing intake and obtain informed consent and authorization for sharing protected health information, intake data and test results.

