All individuals who participate in Aim 2 will be invited to complete an additional longer survey (i.e., "Post-Testing Survey"; 20 minutes) that includes common data element (CDE) questions. This survey will be completed during a future visit to syringe exchange or via e-mail, phone, text, or Facebook.

The target sample size for the RCT in Aim 2 is 350 unique individuals. The RCT will be initiated once IRB approval is received and we anticipate it will take approximately 3-4 months to reach the target sample size. Aim 2 data will be shared with the RADx-UP CDCC as required by our funder. The information that will be shared is summarized in the consent form. We plan to enroll 350 participants.

Data Analysis: We will use a randomized control trial to evaluate whether Connect2Test + Contingency Management increases COVID-19 testing utilization in comparison to contingency management alone. We will also test whether SDOH and key motivational variables (collected via Aim 2 Brief Client Survey) moderate intervention effects. We will use chi-square tests to examine whether the expected rates of testing utilization vary by condition. We will use logistic regression to examine whether SDOHs moderate intervention effects.

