For Phase I & 2, Aim 2 syringe exchange clients, a research staff person will invite syringe exchange service participants to participate in the study when they visit the exchange for services (see Recruitment script). The research staff will inform clients about the opportunity to participate in the research study and obtain signed informed consent. At the time of consent, research staff will ask clients to complete a HIPAA Authorization form for the purpose of releasing their testing and vaccination intake data and test result to the UO research team. The HIPAA form will also be programmed in Qualtrics. UO's COVID-19 MAP will only give the research team access to test results data for HIVA IDs for whom we have a HIPAA authorization and consent. Clients will be given a blank consent and HIPAA form. During the course of the RCT, clients will only be invited to participate in the study once. Research staff will document participation to target recruitment of unique individuals visiting the exchange. Regardless of whether clients consent to participate in the study, they will be offered an opportunity to get tested or vaccinated every time they visit the exchange. The RCT in Aim 2 will be conducted any HIV Alliance syringe exchange site. Clients will receive a \$10 gift card for their participation in the study to be given after completing the Brief Client Survey. All individuals who participate in Aim 2 will be invited to complete an additional longer survey (i.e., 20 minutes) that includes common data element (CDE) questions and “Aim 2 Brief Client Survey” at a future date approximately 3 weeks from the date of enrolling in Aim 2. Clients will be given an appointment reminder card with their 3 week return date and a phone number to reach research staff. This survey will be completed during a future visit to syringe exchange or via e-mail, phone, text, or Facebook. Clients can show up at a syringe exchange event or call the number on their appointment card to make alternate arrangements to complete the survey. We will also

attempt to contact participants if they are unable to make their scheduled appointment and will provide reminder messages. Participants will receive a \$20 gift card for completing this survey. For clients who complete the survey remotely, we will make arrangements with them to disburse payment by meeting at a syringe exchange site, another public location, or mailing it to them.

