Statistical Analysis Plan

Official Title: Motivational Enhancement to Augment Contingency Management for SARS-CoV-2 Testing and Vaccination Utilization Among Syringe Exchange Clients

NCT number: NCT05534061

Document Date: July 26, 2022

Statistical Analysis Plan

Study Title: Creating a Sustainable Infrastructure for SARS-COV-2 Testing at Syringe Exchange Programs

Protocol Number: 11162020.013

Preliminary analyses included a description of the sample and extent of missing data and tests of baseline equivalency of randomized groups. Study participants received the intervention across nine sites resulting in a multilevel data structure. We used multilevel logistic regression estimated with the generalized linear model using the adaptive quadrature quasi-likelihood estimator to compare rates of COVID-19 testing and vaccination administered on the same day of the intervention and anytime during the 9-month follow-up period. A Bernoulli distribution and logit link function were specified, and odds ratios and 95% confidence intervals reported to facilitate interpretation. First, a null model was specified to estimate the variability between sites and within individuals followed by the full model that included the study randomized condition as the predictor (coded 1 = CM + Connect2Test, 0 = CM).

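### Does the SAP need a moderation model because the protocol plans to test social-determinant and motivational moderators?

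*Protocol*

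**What the plan says.** The moderation plan is in the Protocol, section C, under the Data Analysis heading for Phase II, Aim 2. It names two classes of moderator: "We will also test whether SDOH and key motivational variables (collected via Aim 2 Brief Client Survey) moderate intervention effects". The same paragraph gives a method for one class: "We will use logistic regression to examine whether SDOHs moderate intervention effects". The only outcome it names, in the sentences on the arm comparison and the chi-square test, is testing utilisation.

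The SAP is one paragraph. It uses multilevel logistic regression to "compare rates of COVID-19 testing and vaccination administered on the same day of the intervention and anytime during the 9-month follow-up period", which makes four outcome-by-window comparisons. The site structure is the stated reason: "Study participants received the intervention across nine sites resulting in a multilevel data structure". After a null model, the analysis is "followed by the full model that included the study randomized condition as the predictor". No interaction, moderator or subgroup is mentioned.

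The survey that supplies moderators is given twice. In section C, under Intervention testing, "consented participants will complete a brief survey (Aim 2 Brief Client Survey) and be randomized by Qualtrics". In section D, Recruitment Procedures, it is repeated together with the common data element questions "at a future date approximately 3 weeks from the date of enrolling in Aim 2".

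**The concern.** An analysis that the protocol announces but the SAP omits can be left out without comment, or assembled after the data are seen. Four things are open in the supplied text: which social determinants and motivational items are moderators, which outcome and window they apply to, which administration of the survey supplies them, and what model is fitted. The protocol's model sentence covers social determinants only and does not mention site.

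If several moderators were crossed with several outcomes and only the striking result reported, a reader could not tell how many interactions had been tried. Moderators taken from the 3-week survey would be measured after randomisation and only in responders. The stake is the credibility of a claim about who benefits from Connect2Test, not the estimate of whether it works.

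**Working it through.** The documents give no power, event rate, moderator count or effect size for moderation, so there is no stated figure to reproduce. The check has two parts.

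**Reading the texts together**

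1. *Outcome.* The Phase II analysis paragraph names testing utilisation and nothing else, so that is the natural outcome for its moderation tests. Vaccination enters through Aim 2b and the SAP, not through this paragraph. The choice between same-day and 9-month testing stays open.
2. *Timing of the moderators.* The enrolment survey is listed before randomisation. A moderator of a randomised effect is ordinarily a baseline variable, so this is the administration an analyst would use.
3. *Motivational variables without a model.* One sentence plans both moderator classes. The sentence on social determinants alone repeats the Phase I Data Analysis wording exactly. It reads as carried-over text, not as a decision to leave the motivational variables unmodelled.
4. *Logistic or multilevel logistic.* The SAP's model is a logistic regression that also handles site. Adding a condition-by-moderator term to it satisfies both documents.

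**Size, as an illustration**

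Assumptions not in the documents: two moderators in each class (the smallest number the plurals allow), two-sided 5% tests, 1:1 allocation, 50:50 binary moderators, no clustering or dropout, testing rates of 20 to 50%. From the protocol: 350 participants.

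Chance of at least one false positive with k independent tests, 1 − 0.95^k:

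| Scope | k | Result |
|---|---|---|
| Testing, one window | 4 × 1 = 4 | 0.185 |
| Testing, both windows | 4 × 2 = 8 | 0.337 |
| All four SAP outcomes (worst case) | 4 × 4 = 16 | 0.560 |

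Positive correlation among the tests lowers these figures. The last row adds vaccination outcomes that the protocol's analysis paragraph does not name.

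Precision of one interaction: there are four cells of 350/4 = 87.5, each log odds having variance 1/(87.5·p(1−p)). The four variances add, so SE = 4/√(350·p(1−p)). Power for an interaction odds ratio of 2.0 is Φ(ln 2/SE − 1.96). The smallest significant odds ratio is exp(1.96·SE), and the odds ratio needed for 80% power is exp(2.802·SE).

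| p | SE | Power at OR 2.0 | Smallest significant OR | OR for 80% power |
|---|---|---|---|---|
| 0.20 | 0.535 | 0.254 | 2.85 | 4.47 |
| 0.30 | 0.467 | 0.318 | 2.50 | 3.70 |
| 0.50 | 0.428 | 0.367 | 2.31 | 3.31 |

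These two tables should not be set directly against each other. The first gives an error rate over a family of tests; the second gives the power of a single test. Like with like, a single test has a 5% false-positive rate against 25 to 37% power. For four independent tests, each with a true odds ratio of 2.0, the chance of at least one detection is 1 − 0.746⁴ = 0.69 to 1 − 0.633⁴ = 0.84, against 0.185 for a false positive. It would be wrong to say that a chance moderator is as likely to appear as a real one is to be found.

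**The case for a change.** The best case for a change is that the protocol commits to this analysis and the SAP is the only other analysis document supplied, so its silence leaves a reader unsure whether moderation was kept, dropped or selected. The natural reading settles the timing, but not the list of items. The source of the social determinants is the weakest link: the bracket in the protocol may cover only the motivational variables, and the Phase I text describes "the moderating effects of SDOHs (assessed using the CDEs and HIVA intake data" in parentheses. In Phase II the common data elements come in the later survey, and the intake form is completed at testing or vaccination, so moderators drawn from that form would depend on the outcome. One SAP paragraph would deal with all of this.

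Much of this stands as fact. The SAP is silent, no item is named in the supplied text, and a moderator list would be good practice. But the worry about the source is conditional: the Phase I source is not restated for Phase II, and the survey instruments, which are not supplied, may contain the items. Moderation is also absent from the wording of Aim 2b. It is explicit only in the Phase I aim, which the Phase II aims are said to mirror.

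The SAP is written in the past tense. If the analyses have been run, a list added now would not restore pre-specification. Labelling a result as not pre-specified would also misstate the record, because the protocol does plan the test, the two classes of moderator, the survey for at least the motivational ones, and logistic regression for the social determinants.

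**Conclusion.** The gap is real but calls for no change to the plan. It concerns the detail of a secondary analysis that competent analysts would fill in the same way: baseline moderators, testing as the outcome, and an interaction term in the site-level model already chosen. The randomised comparison of the two arms is unaffected, and no result has been shown to change.

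The figures show why moderation should be read as exploratory in any event: 25 to 37% power for an interaction odds ratio of 2.0, with an odds ratio of 3.3 to 4.5 needed for 80% power. Naming the variables would not improve either figure. The chance of a false positive somewhere is 19 to 34% for testing outcomes, and 56% only in the worst case that adds vaccination. All of these rest on an assumed four 50:50 moderators, equal arms, independent tests, no clustering and testing rates of 20 to 50%, none of which the documents state.

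A reader who meets a moderation result from this trial can fairly describe it as planned in the protocol, with the specific variables and model not set out in the documents supplied.
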